A prospective randomized trial comparing Restorelle® Y mesh vs. Vertessa® lite Y mesh for laparoscopic and robotic-assisted laparoscopic sacrocolpopexy

[name] MPH; Assistant Professor of Surgery. Center for Urogynecology and Pelvic Reconstructive Surgery; Obstetrics/Gynecology and Women's Health Institute, Cleveland Clinic, Cleveland OH

[name] [name]; Professor, Section Head of the Center for Urogynecology and Pelvic Reconstructive Surgery; Obstetrics/Gynecology and Women's Health Institute, Cleveland Clinic, Cleveland OH

Background and Significance:

Abdominal sacrocolpopexy is considered the gold standard for vault prolapse, and has demonstrated superior anatomic outcomes compared to transvaginal suspension procedures. Laparoscopic sacrocolpopexy has become an alternative to open abdominal sacrocolpopexy as this mode of surgery bridges the gap between the advantages of vaginal surgery, namely decreased morbidity and faster patient recovery, with the surgical success rates of abdominal sacrocolpopexy (1). For young women who are sexually active with symptomatic pelvic organ prolapse, reconstruction with a sacrocolpopexy procedure is beneficial because the success rates are high as the procedure adequately restores support of the vaginal apex and maintains vaginal length (2). Robotic-assisted laparoscopic sacrocolpopexy has also emerged as a mode of vaginal vault prolapse surgery, and is a good option for patients with significant body mass index, or known pelvic adhesive disease that may make a conventional laparoscopic approach more challenging.

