- Other concomitant laparoscopic or prolapse and anti-incontinence procedures (e.g., laparoscopic supracervical hysterectomy, cystocele repair, rectocele repair or mid-urethral sling procedures) will be performed at the primary surgeon's discretion.

Exclusion Criteria:

- Inability to comprehend written and/or spoken English
- Inability to provide informed consent
- Medical illness precluding laparoscopy
- Need for concomitant surgeries not related to pelvic organ prolapse or incontinence
- Sacrocolpopoperineopexy
- Need for dual flat mesh for sacrocolpopexy procedure (determined by surgeon)

Study Procedures:

Study Identification and Recruitment

Potential subjects will be identified by members of the Center for Urogynecology & Pelvic Reconstructive Surgery at the Cleveland Clinic Main campus and Fairview Hospital. Eligible patients that agree to participate will be provided written informed consent administered by the collaborators listed on this IRB.

Randomization

All subjects will be predetermined by their surgeon to undergo either a laparoscopic or robotic assisted laparoscopic sacrocolpopexy depending upon their clinical evaluation. The participants will then be randomized to either Restorelle® or Vertessa® Y sacrocolpopexy according to a computer-generated randomization schedule with random block sizes with the use of the SAS statistical software package (SAS Institute, Cary, NC). All patients will be blinded to their assignment.

Office Interventions

All patients will be seen for a preoperative visit and then postoperatively at 6, 12 and 24 months. At each visit, a vaginal exam and a complete Pelvic Organ Prolapse Quantification (POP-Q) exam will be performed. Patients will also be asked to update their medical history. In addition, patients will be asked to complete the Pelvic Floor

Distress Inventory (PFDI-20), Incontinence Severity Index (ISI) and Pelvic Organ Prolapse/Urinary Incontinence Sexual Questionnaire (PISQ-12) questionnaires at the pre-operative visit as well as the 6, 12, and 24 month postoperative visits. Completion of these questionnaire is the only additional assessment that is specific to participation in this study and is not usually included as part of the standard care of sacrocolpopexy. It should take no more than 10-15 minutes to complete the questionnaires. The study subjects will not be exposed to any additional risk by participating in this study except for the inconvenience of completing the questionnaire.

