The sacrocolpopexy will also be performed and in a standard fashion. An end-to-end anastomosis (EEA) sizer will be placed in the vagina for manipulation of the apex as well as in the rectum for delineation of the rectovaginal septum. First, the presacral dissection will be performed with a longitudinal peritoneal incision over the sacral promontory and there is identification of the anterior longitudinal ligament. Dissection is then done caudally through the peritoneum and subperitoneal fat down to the level of the posterior cul-de-sac. The vagina is elevated cephalad using the EEA sizer and the peritoneum overlying the anterior vaginal apex is incised transversely, and the bladder is dissected off the anterior vagina using sharp dissection, creating a 4 to 5 cm pocket. If this plane is difficult to establish, the bladder will be filled in a retrograde fashion to find the correct dissection plane. Similarly, the peritoneum overlying the posterior vagina is incised, and dissection is then done overlying the vagina and extending into the posterior cul-de-sac, creating a 4 to 5 cm pocket. Once dissection is complete, the mesh graft is prepared. Subjects will have been randomized to either one of two mesh grafts:

The Y mesh is introduced into the pelvis through one of the ports. First, either the anterior or the posterior arm is fixed to the anterior or posterior vaginal wall using 6

delayed-absorbable (PDS) No. 2-0 sutures in an interrupted fashion, 1 to 2 cm apart from each other. The opposing arm of the graft is then attached to either the anterior or posterior vaginal wall, depending on which arm was placed first, in a similar fashion using 6 delayed-absorbable (PDS) No. 2-0 sutures in an interrupted fashion, 1 to 2 cm apart from each other. The stem portion of the graft is then brought to the sacral promontory and sutured to the anterior longitudinal ligament using 2 permanent (prolene) No. 0 sutures. The excess mesh is then trimmed.

The peritoneum is then closed over the exposed graft with absorbable suture. Routine cystoscopy will also be performed in order to assess for lower urinary tract injury. A vaginal exam is performed, and an anterior and/or posterior colporrhaphy and perineorrhaphy are performed if needed. Anti-incontinence procedures may also be performed if needed.

**In laparoscopic cases, all suturing will be done extracorporeally while intracorporeal knot-tying technique will be performed in robot assisted laparoscopic cases.

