There will be 2 arms to this study: laparoscopic (robotic-assisted and conventional) sacrocolpopexy with Restorelle® Y mesh and laparoscopic (robotic-assisted and conventional) sacrocolpopexy with Vertessa® Y mesh. Subjects will be chosen based on surgeon preference to either undergo RA LSC ASC or conventional LSC ASC. They will then be randomized to either the Restorelle® or Vertessa® Y mesh arm. We determined that if there is no difference between the two Y mesh grafts, 90 patients are required to be 70% sure that the upper limit of a one-sided 95% confidence interval will exclude a difference in favor of the Restorelle® group of more than 10%. We will account for a potential 10% subject drop out and loss to follow-up as well as unforeseen factors in recruiting and will plan to recruit 50 subjects to each arm, for a total of 100 subjects.

All statistical analyses will be done using jmp 12. We will use descriptive statistics to show our demographic and baseline data: categorical variables will be presented as n/N (%) with 95% confidence intervals and continuous variables will be presented as mean +/-SD [range]. The two Y mesh grafts will be compared. Differences between the groups in the primary outcome of surgical success and other categorical outcomes were evaluated using generalized linear models. We will control for LSC ASC and RA LSC ASC by performing a logistic regression.

Summary of tasks for study:

	Preop	6 mo	12 mo	24 mo
Informed consent	X			
Demographic data	X			
Randomization	X			
PFDI-20	X	X	X	X
ISI	X	X	X	X
PISQ-12	X	X	X	X
POP-Q	X	X	X	X
Review of d/c summary, chart, postop Hct, complications (ER visits, etc)		X		
Update medical history		X	X	X

References:

3. Porges RF & Smilen SW. Long term analysis of the surgical management of pelvic floor support defect. *Am J Obstet Gynecol* 1994;171:1518–1528.
4. Birch C. The use of prosthetics in pelvic reconstructive surgery. *Best Pract Res Clin Obstet Gyn* 2005;19(6):979-991.
5. Chu CC & Welch L. Characterisation of morphological and mechanical properties of surgical mesh fabrics. *J Biomed Res* 1985;19:903–916.
6. Kaupp HA, Matulewicz TJ & Lattimer GL. Graft infection or graft reaction? *Arch Surg* 1979;114:1419-1423.

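### Surgical route is fixed before randomization and is the only factor adjusted for, but no stratification by route is described and the adjusted result is not on the margin's scale: a cheap improvement

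*Combined protocol and SAP*

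**What the plan says.** The Randomization section sets the order of events: "All subjects will be predetermined by their surgeon to undergo either a laparoscopic or robotic assisted laparoscopic sacrocolpopexy depending upon their clinical evaluation". Mesh is then allocated "according to a computer-generated randomization schedule with random block sizes", produced in SAS. Neither that section nor the Analysis Plan names a stratification factor.

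The Analysis Plan repeats the order: "Subjects will be chosen based on surgeon preference to either undergo RA LSC ASC or conventional LSC ASC", followed by "They will then be randomized to either the Restorelle® or Vertessa® Y mesh arm". On adjustment it says: "We will control for LSC ASC and RA LSC ASC by performing a logistic regression". No other covariate is named. Groups are to be compared on the primary outcome with generalized linear models, for which no link function or effect measure is given. The sample size statement uses a one-sided 95% confidence limit and a margin of 10%, on the difference scale.

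Two other places bear on what route stands for. Background and Significance says that the robotic approach "is a good option for patients with significant body mass index, or known pelvic adhesive disease". Surgical Interventions adds a difference in technique: "In laparoscopic cases, all suturing will be done extracorporeally while intracorporeal knot-tying technique will be performed in robot assisted laparoscopic cases".

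**The concern.** Route is binary, known at the moment of allocation, and the one variable the plan itself chose to control for. It carries patient selection, surgeon preference and a difference in suturing technique. That makes it the natural stratification factor, and the described schedule does not use it. A chance imbalance in route would then have to be dealt with in the analysis.

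The analysis tool is awkward for that job in two ways. Logistic regression returns an odds ratio, while the margin is a 10-point risk difference, and the plan does not say how one is compared with the other. Failures will also be few, so the model may have no finite estimates. At stake is whether the adjusted analysis can support the non-inferiority claim, and, to a smaller extent, whether the raw difference in this one trial is disturbed by route.

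**Working it through.** **Inputs from the documents (Analysis Plan; Background and Significance).** 90 evaluable and 100 recruited patients, 50 per arm; margin 10 points; one-sided 95% limit; 70% power; no true difference. Success reported for the Restorelle mesh in the cited prospective series: 89% anatomic, 94% subjective.

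**Assumptions.** The documents give no robotic share (taken as 20% to 50%), no effect of route on failure (10 points used for illustration) and no planning success rate.

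**1. The plan's own figure.** n per arm = (z₀.₉₅ + z₀.₇₀)² × 2p(1 − p) / 0.10², where (1.645 + 0.524)² = 4.706.
- p = 0.95: 4.706 × 0.095 / 0.01 = 44.7, so 45 per arm and 90 in total. This matches.
- p = 0.94: 53.1, so 54 per arm and 108 in total.
- p = 0.89: 92.1, so 93 per arm and 186 in total.

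The stated 90 is therefore reproduced with an assumed success rate of 95%. Dropout: 90 / 0.90 = 100, which matches.

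**2. Route imbalance without strata.** With K robotic cases among 100 and 50 per arm, the number k in one arm is hypergeometric, and the gap in robotic share is |2k − K| / 50. Its SD is (2/50) × √[50 × f(1 − f) × 50/99], with f = K/100.

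| Robotic share | SD of gap (points) | P(gap ≥ 10 points) | P(gap ≥ 20 points) |
|---|---|---|---|
| 20% | 8.0 | 21% | 2% |
| 30% | 9.2 | 28% | 5% |
| 50% | 10.1 | 32% | 7% |

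**3. What a gap does to the raw difference.** Shift = gap × route effect. With a 10-point route effect: 0.10 × 10 = 1 point for a 10-point gap, and 0.20 × 10 = 2 points for a 20-point gap. The standard error of the difference at 45 per arm is √[2p(1 − p)/45] = 4.6 points at 95% success and 6.6 points at 89%.

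**4. Operating characteristics.** Simulation with 45 per arm, 30% robotic, 95% success and a 10-point route effect; unadjusted test:

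| True difference | Non-inferiority declared, unstratified | Stratified |
|---|---|---|
| 0 | 70.9% | 71.3% |
| 10 points | 7.0% | 6.7% |

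**5. Sparsity.** Expected failures among 90: 90 × 0.05 = 4.5, 90 × 0.06 = 5.4, 90 × 0.11 = 9.9.
- Chance that a whole arm or a whole route has no failure, so that some coefficient of the main-effects logistic model has no finite estimate: 28% to 47% at 5% failure and 2% to 13% at 11% failure, for robotic shares of 50% down to 20%.
- Chance that the mesh coefficient itself has no finite estimate because a mesh arm has no failure: 2 × 0.95⁴⁵ − 0.95⁹⁰ = 18.9% at 5% failure, and 2 × 0.89⁴⁵ − 0.89⁹⁰ = 1.1% at 11% failure. This does not depend on route.
- Effect of stratifying, at 5% failure and 30% robotic: 35.7% unstratified against 35.9% stratified for the arm-or-route figure.

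**The case against.** The strongest reply is that unstratified block randomization is valid. Chance imbalance is part of the sampling error that the confidence interval already covers, and step 4 shows that stratifying moves the decision probabilities by only 0.3 to 0.4 points. This stands, and it is why the point is minor.

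Second, the documents do not say that route predicts surgical failure. A reader might infer that it does, because robotic surgery is linked to high BMI and adhesions. But the text ties these to the difficulty of a conventional approach, not to recurrence, and it also makes route a matter of surgeon preference. The 10-point route effect is an illustration. It is a large one: at 5% overall failure and a 30% robotic share it means about 2% against 12% failure. Even combined with an unlikely 20-point gap, the 2-point shift is less than half a standard error.

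Third, a reader might use the sparse model as an argument for stratified randomization. Step 5 does not support that. Few failures follow from the event rate and the sample size, and stratifying leaves separation unchanged. When only a route has no failures, the route coefficient diverges but the mesh coefficient can stay finite. Sparsity and effect scale belong to the analysis and need their own remedy.

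Fourth, a reader might take it as established that the list is unstratified. The protocol is silent: it neither states nor excludes separate lists by route.

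One further allowance: the plan's generalized linear models could be fitted on the risk-difference scale. The plan does not say so, and the only sentence on adjustment names logistic regression.

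**Conclusion.** The point holds as a low-severity, cheap improvement. Route is known before allocation and is the sole adjustment factor, yet no stratum is described. An unstratified list would give a 21% to 32% chance of a gap of at least 10 points in robotic share and a 2% to 7% chance of at least 20 points, for an assumed robotic share of 20% to 50%. The likely consequence is small: no bias on average, a shift of 1 to 2 points in a single trial under an assumed 10-point route effect, and almost no change in power or type I error. The documents do not support a claim that the comparison is biased or invalid, or that route is prognostic.

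The analysis part is distinct and does not depend on how the list was made. An odds ratio from logistic regression cannot be compared directly with a 10-point risk-difference margin. With about 5 to 10 expected failures (success of 95% down to 89%), the model can fail to give finite estimates; for the mesh effect itself the chance is 18.9% at 5% failure and 1.1% at 11%.

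**What to change.** 1. **Randomization section.** State whether the blocks are stratified by route. If they are not and allocation has not started, generate the SAS schedule in two strata (conventional laparoscopic; robotic-assisted), with random block sizes within each.
2. **Analysis Plan.** Base the one-sided 95% non-inferiority limit on a route-stratified risk difference with Mantel-Haenszel weights and a score-type or other small-sample interval. Keep the logistic regression as a supportive analysis. Specify this before outcomes are compared by arm. It is worth doing whether or not the list is stratified.

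Cost: two lists in place of one, a few changed sentences and slightly more analysis work, including a check that the named analysis package can produce the interval. The sample size stays at 90 evaluable and 100 recruited. The one downside is that arm totals may differ by a few patients if the last block in each stratum is incomplete.

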In our urogynecology practice at Cleveland Clinic, we currently routinely use the Restorelle® Smartmesh and we have experienced good clinical outcomes using this graft. This mesh seems to have been widely adopted by many surgeons performing sacrocolpopexy. To our knowledge, the only prospective study that exists looking at this mesh at the time of sacrocolpopexy was published by Salamon et al. (7) in 2013 in the International Urogynecology Journal. In this study, the authors sought to prospectively evaluate the use of Restorelle® Y mesh for robotic sacrocolpopexy. They implanted a total of 120 patients and obtained one year follow-up data from 118 of these patients. They reported an anatomic success rate of 89%, a subjective cure rate of 94% and no mesh erosions. Currently no prospective data exists on the Vertessa® lite mesh for sacrocolpopexy. It is used by many surgeons, but there are no data showing that it is as efficacious in treating prolapse and avoiding mesh erosion in those patients undergoing sacrocolpopexy. Therefore, the primary objective of the proposed study is to compare outcomes between the Restorelle® Y mesh and Vertessa® lite Y mesh at the time of laparoscopic and robotic-assisted laparoscopic sacrocolpopexy.

Hypothesis: Vertessa® lite Y mesh is not inferior to Restorelle® Y mesh for the treatment of vaginal vault prolapse.

Study Design: Randomized single-blind non-inferiority trial

Primary Outcome:

Composite outcome measure of surgical success:

- (1) descent of the vaginal apex more than one-third into the vaginal canal
- (2) anterior or posterior vaginal wall descent beyond the hymen
- (3) bothersome vaginal bulge symptoms
- (4) retreatment for prolapse by either surgery or pessary

Secondary Outcomes:

1. Intraoperative, peri-operative and post-operative complications
2. Pelvic floor symptoms (urinary, bowel, prolapse, sexual function): PFDI, ISI, PISQ)
3. Retreatment for urinary incontinence

Study Population: Study subjects will be recruited from patients that present to the Center for Urogynecology & Pelvic Reconstructive Surgery in the Department of Obstetrics and Gynecology at the Cleveland Clinic Main campus, Hillcrest Hospital and Fairview Hospital, and their surgeries will be performed at either one of these sites.

Inclusion Criteria:

- Age ≥ 18 , who are to undergo laparoscopic or robotic laparoscopic sacrocolpopexy for pelvic organ prolapse

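### The protocol says participation adds no risk beyond the questionnaires, but by its own account the relative risk of the two meshes is unknown, and mesh exposure is recorded only if it leads to reoperation.

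*Combined protocol and SAP*

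**What the plan says.** **Risk of participation.** Study Procedures, Office Interventions, says of the questionnaires: "Completion of these questionnaire is the only additional assessment that is specific to participation in this study". The paragraph ends: "The study subjects will not be exposed to any additional risk by participating in this study except for the inconvenience of completing the questionnaire".

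**Mesh outside and inside the trial.** Background and Significance says of the practice: "we currently routinely use the Restorelle® Smartmesh and we have experienced good clinical outcomes using this graft". Of the other mesh it says: "Currently no prospective data exists on the Vertessa® lite mesh for sacrocolpopexy", and adds that "there are no data showing that it is as efficacious in treating prolapse and avoiding mesh erosion in those patients undergoing sacrocolpopexy". Under Randomization: "The participants will then be randomized to either Restorelle® or Vertessa® Y sacrocolpopexy according to a computer-generated randomization schedule". The Analysis Plan sets 50 women per arm.

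**Evidence for the routine mesh.** One prospective robotic cohort is cited: "They implanted a total of 120 patients and obtained one year follow-up data from 118 of these patients". Its results: "They reported an anatomic success rate of 89%, a subjective cure rate of 94% and no mesh erosions".

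**Safety data.** Complications are the first secondary outcome. A vaginal exam is scheduled at 6, 12 and 24 months. Data Collection & Management lists intraoperative complications and a review of the medical record for postoperative ones. Mesh exposure appears in that list only as a cause of reoperation, and it is not a component of the primary composite.

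**The concern.** The risk statement counts only the questionnaires as a consequence of joining. Joining also changes how a permanent implant is chosen: a woman who would routinely have received Restorelle at this site has an even chance of receiving Vertessa lite. The protocol justifies the trial by saying that the relative performance of the two, including on erosion, has not been shown. It cannot also assert that assignment carries no added risk.

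Two gaps in the safety plan bear on the same unknown. An exposure seen at a scheduled exam and handled without reoperation has no listed data item, so the trial could under-record the event it names as an evidence gap. And the supplied text does not say that anyone compares accumulating complications between arms while women are still being randomized.

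**Working it through.** **1. Number of women concerned.** The Analysis Plan gives 90 evaluable patients and 10% dropout: 90 / (1 − 0.10) = 100, or 50 per arm. This reproduces the plan's figure. It counts women allocated to Vertessa, not women harmed.

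**2. The statements side by side.**
- Office Interventions: no added risk except questionnaire inconvenience.
- Background: Restorelle is routine here; no prospective data on Vertessa lite in sacrocolpopexy; no data showing it is as good on prolapse or erosion.
- Randomization: the mesh is set by a computer-generated schedule.
- Analysis Plan: the trial is sized to exclude a difference of more than 10% in favor of Restorelle, so the design treats inferiority as possible.

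The last three make the risk difference an open question. The first closes it at zero.

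**3. What zero events can show.** The exact one-sided 95% upper limit for 0 of n is 1 − 0.05^(1/n).
- Cited Restorelle cohort, n = 118: 1 − 0.05^(1/118) = 2.5%.
- One full arm, n = 50: 1 − 0.05^(1/50) = 5.8%.
- One arm after 10% loss, n = 45: 1 − 0.05^(1/45) = 6.4%.

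An event-free Vertessa arm would thus not bound erosion as tightly as the cited cohort does for Restorelle.

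**4. Why incomplete capture matters.** The chance of at least one event in 50 is 1 − (1 − p)^50. The documents give no Vertessa rate, so p is assumed: 39% at p = 1%, 64% at 2%, 78% at 3%, 92% at 5%. The share of exposures handled without reoperation is not stated either. If the true rate were 2%, the chance of recording at least one event would be 64% if every exposure led to reoperation, 39% if half did (recorded rate 1%), and 0% if none did.

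**5. What a tally during enrolment could do.** Take at least 2 exposures among n fully followed Vertessa patients, as an illustration and not as a proposed trigger: P = 1 − (1 − p)^n − np(1 − p)^(n−1).
- n = 20: 26% at p = 5%, 61% at p = 10%.
- n = 12 to 13 (about half of the first 25 randomized): 12–14% at 5%, 34–38% at 10%.

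The first scheduled postoperative visit is at 6 months and no accrual rate is given. How many women would have been examined before randomization ends cannot be derived.

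**The case against.** The best defense is that the Background describes both meshes as ultra-light macroporous polypropylene, made for pelvic floor reconstruction and both currently used for sacrocolpopexy, and says many surgeons use Vertessa. It reports missing data, not higher risk. The challenged sentence also closes a paragraph about questionnaires, which partly explains its wording. All of this stands, and it limits the point to an unsupported assurance. It does not rescue the sentence, because similarity of class is not the comparative evidence that the same section says is lacking.

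A reader might infer more than the documents support:
- *That women are misinformed at consent.* The consent form is not in the supplied text, and whether it repeats the sentence is unknown.
- *That nothing is monitored.* Complications, record review, vaginal exams and reoperations are all collected. What is missing is a described review of accumulating data.
- *That an excess would come to light only after every implant is placed.* Patients and the POP-Q examiner are blinded; the surgeons are not described as blinded. Nothing prevents exposures or reoperations from being noticed during enrolment.
- *That Vertessa lite is riskier.* No passage says so.

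It can also be said that by-arm review in a 100-patient comparison of two meshes already in use breaches no standard set in the protocol. That is fair. The review is a modest safeguard, and its early value is uncertain (working, step 5).

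**Conclusion.** The concern holds in a limited form. The no-added-risk sentence is not supported by the protocol's own background once randomization sets the mesh. The accurate statement is that comparative risk is unknown. This applies to the 50 of 100 women planned for Vertessa, on the assumption that they would otherwise have received the mesh the site calls routine.

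Exposure without reoperation lacks a listed item, and no by-arm review of accumulating complications is described. Both statements rest on the supplied text, in which a figure after the postoperative list is not shown. The 5.8% limit assumes all 50 women are assessed with no event. The other probabilities rest on assumed rates and do not predict what this trial will see. The correction to the sentence needs none of these figures.

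**What to change.** 1. **Risk statement.** Replace the sentence in Office Interventions with one saying that randomization may assign a mesh other than the one routinely used at the center, and that relative erosion and efficacy risk is unknown. Check that the consent form agrees.
2. **Data item.** Add a REDCap field for mesh exposure found at the 6, 12 and 24 month vaginal exams, whether or not it led to reoperation. Report it by arm with exact confidence limits.
3. **Review during enrolment.** Name a person who neither operates on nor examines participants to send a by-arm tally of exposures and reoperations to the IRB at set points. The investigators should fix in advance the count that prompts a review. The tally should not go to the clinicians listed at the front of the protocol, who may operate or examine.

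The cost is one added data item, a few short reports, a wording amendment and a slightly less favourable risk statement. No visits or patients are added. How early the tally could signal depends on accrual, which should be stated alongside it.

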Data Collection & Management:

Preoperative data will include the following:

- Patient age, race, vaginal parity, menopausal state, BMI, prior prolapse surgery, preoperative prolapse stage
- PFDI-20, ISI, PISQ-12
- Preoperative hemoglobin

Data points recorded during the procedure will include:

- Total OR time = operating room time of entry and exit
- Total Case time = time from incision to closure
- Concomitant procedures
 - Supracervical hysterectomy
 - Anterior colporrhaphy
 - Posterior colporrhaphy
 - Perineorrhaphy
 - Midurethral sling
- Estimated blood loss
- Intraoperative complications
 - EBL > 500cc
 - Vascular Injury
 - Cystotomy
 - Ureteral Injury
 - Bowel Injury - small bowel, large bowel, rectal

Postoperative data will include the following: 6, 12, 24 months

- POP-Q exam (performed by a provider blinded to the mesh used at the time of the procedure)
- PFDI-20, ISI, PISQ-12

- Review of electronic medical record (inpatient notes, d/c summary, ER visits), assessing for postoperative complications
 - Reoperation for immediate complications = reoperation within 30 days of surgery
 - Abdominal Wound infection = fascial, subcutaneous, cutaneous infection requiring antibiotic treatment
 - Hematoma = intrapelvic/abdominal
 - Vaginal cuff cellulitis/Pelvic Abscess = requiring IV/PO antibiotic therapy and/or transvaginal, transgluteal or percutaneous drainage
 - DVT/PE = diagnosed with Doppler US or CT scan
 - Reoperation for SUI with pubovaginal sling (synthetic or fascial), colposuspension, injection with periurethral bulking agents
 - Reoperation for mesh exposure
 - Reoperation for recurrent POP
 - Bowel Injury/Bowel Obstruction = enterotomy, perforation, ileus, partial/complete obstruction
 - Port site or incisional hernia
 - Need for any radiologic imaging
 - Lower urinary tract injury = bladder, ureteral
 - Neurologic Injury = brachial plexus, abdominal wall (ilioinguinal, iliohypogastric), lower extremity (femoral, sciatic, common peroneal)
 - Pulmonary complications = pneumonia, pulmonary hypertension, pulmonary edema within 14 days of surgery
 - Cardiac = ACS, MI, HF within 14 days of surgery
 - Postoperative ICU admission

[figure not shown]

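### With a logit link, the models planned for complications give no finite odds ratio when exactly one arm has no events, and the plan names no link, test or zero-cell rule

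*Combined protocol and SAP*

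**What the plan says.** The Analysis Plan gives one between-arm method for categorical data: surgical success and "other categorical outcomes were evaluated using generalized linear models". It then adds: "We will control for LSC ASC and RA LSC ASC by performing a logistic regression". It states no link for the first model, no effect measure, no choice between Wald, likelihood-ratio and exact tests, and no rule for empty cells. Its sentence on n/N with 95% confidence intervals concerns demographic and baseline data.

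The first secondary outcome is "Intraoperative, peri-operative and post-operative complications". Data Collection & Management lists these singly. The items include ureteral and bowel injury, DVT/PE, intensive-care admission and "Reoperation for mesh exposure". The document does not say whether they will be compared one by one or pooled.

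The only complication rate given is in Background and Significance, where a cohort with one-year data on 118 women had "a subjective cure rate of 94% and no mesh erosions". Of the other mesh, the same section says that "there are no data showing that it is as efficacious in treating prolapse and avoiding mesh erosion".

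On size, the Analysis Plan states that "90 patients are required to be 70% sure" and plans to "recruit 50 subjects to each arm, for a total of 100 subjects".

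**The concern.** A logistic model needs at least one event and one non-event in each arm to give a finite arm effect. When one arm has no events, the likelihood keeps rising as the log odds ratio grows, so the printed estimate and standard error depend only on where the software stops. The tests from that fit then disagree sharply. Single complications in a trial of this size are where an empty arm is likely. Avoiding erosion is part of why the trial is being done, and reoperation for exposed mesh is a separate item. For such an item the stated method could give no usable effect estimate, and a p-value that depends on a test chosen after the counts are known.

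**Working it through.** **Inputs.** From the Analysis Plan: 90 evaluable women, 10% dropout, 100 recruited. 90/(1 − 0.10) = 100 reproduces the recruitment figure, and 90/2 = 45 per arm. From the background: 0 erosions in 118 women, with an exact one-sided 95% upper limit of 1 − 0.05^(1/118) = 2.5% (3.1% for a two-sided interval). The plan gives no other complication rate, so the rates below are assumptions, taken as equal in both arms unless stated.

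**Step 1: how often exactly one arm is empty.** With q = (1 − r)^45, the probability is 2q(1 − q).
- r = 1%: q = 0.636, giving 46%.
- r = 2%: q = 0.403, giving 48%.
- r = 3%: q = 0.254, giving 38%.
- r = 5%: 18%. r = 10%: 2%.

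**Step 2: the logit fit for 0/45 vs 6/45.** The log odds ratio is 9.7, 24.7 and 31.7 after 10, 25 and 50 iterations. The standard error is 29, about 53,000 and about 1.8 million, and the Wald p-value is 0.74, 0.9996 and 1.0000. There is no finite estimate, and the Wald test cannot reject. Fisher's two-sided p for the same table is 2 × C(45,6)/C(90,6) = 0.026.

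**Step 3: the other tests on 0/45 vs 4/45.** The pooled rate is 4/90 = 0.0444.
- Likelihood ratio: 2 × [4 ln 2 + 45 ln(1/0.9556) + 41 ln(0.9111/0.9556)] = 5.73, p = 0.017.
- Score (Pearson): (4/45)² / (0.0444 × 0.9556 × 2/45) = 4.19, p = 0.041.
- Fisher: 2 × C(45,4)/C(90,4) = 0.117.
- Miettinen-Nurminen 95% interval for the risk difference: 0.6 to 20.8 points.

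**Step 4: true error of nominal two-sided 5% tests,** by full enumeration of the two binomials, 45 per arm.

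| True rate | Likelihood ratio | Wald | Score | Fisher |
|---|---|---|---|---|
| 1% | 1.3% | 0.0% | 0.1% | 0.0% |
| 2% | 4.9% | 0.0% | 1.0% | 0.0% |
| 3% | 7.9% | 0.0% | 2.5% | 0.1% |
| 4% | 9.1% | 0.0% | 3.9% | 0.3% |
| 5% | 9.0% | 0.1% | 4.9% | 0.6% |
| 10% | 6.2% | 1.8% | 5.9% | 2.0% |

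Over rates from 1% to 10% the score test ranges from 0.1% to 6.0%.

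**Step 5: power for a true 0.5% vs 10%.** Wald 1%, Fisher 25%, score 59%, likelihood ratio 73% (the last with the inflated error shown above).

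**Step 6: 50 per arm,** which suits intraoperative items seen before any dropout. Exactly one arm is empty with probability 48%, 46% and 34% at 1%, 2% and 3%. Likelihood-ratio error is 1.7%, 5.8%, 8.5% and 8.8% at 1%, 2%, 3% and 5%. The picture is the same.

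**The case against.** The strongest reply is that a generalized linear model does not fail as such. Non-finiteness depends on the link, and none is stated for the unadjusted comparison. The primary margin is in percentage points, so an identity link is a fair guess; under it, 0/45 vs 4/45 is a finite 4/45 = 8.9 points. This stands, and a reader should not infer that every such model breaks down. But the plan names no identity link, and its one explicit binary model is logistic. An identity-link Wald interval also has zero width when both arms are empty.

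A reader might also infer that the same analysis can err in both directions. It cannot: the Wald test hides differences, the likelihood-ratio test overstates them, and the plan names neither. Nor is the likelihood-ratio test inflated at 1% to 2% with 45 per arm, where empty arms are commonest. Of the tables with exactly one empty arm, 97%, 90% and 80% (at 1%, 2% and 3%) are 0 vs 1 or 0 vs 2, where no test is significant at 5%. In those tables the missing estimate and interval are the problem, not a wrong decision.

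Three further limits stand. Some listed items, such as the need for imaging, may not be rare. If complications were pooled at about 10%, exactly one empty arm would occur about 2% of the time; the plan does not provide for pooling, and pooling would not answer the question about mesh exposure. Finally, a diverging odds ratio is visible in the output, and the raw counts can still be reported.

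**Conclusion.** The concern holds for complications compared singly on a logit scale. At assumed rates of 1% to 3%, a comparison has between a 38% and a 48% chance of leaving exactly one arm empty, and then no finite odds ratio or Wald interval exists. The Wald test is then powerless, and the likelihood-ratio test runs at 7.9% to 9.1% when the true rate is 3% to 5%. This is more than missing detail, because the one link that the plan does name gives unusable or miscalibrated results in tables that it should expect.

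The conclusion rests on assumed event rates (only 0/118 erosions is documented), on 45 evaluable women per arm, and on item-by-item comparison. A reader might infer that the trial's main conclusion is at risk, or that the plan would declare the meshes equally safe. The documents support neither: complications are secondary outcomes with no stated alpha or decision rule, and the plan makes no equal-safety claim. The primary non-inferiority conclusion is not affected.

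**What to change.** For complications and reoperations, replace the generalized linear model with these rules:
- Report n/N per arm with Clopper-Pearson 95% limits.
- Report the risk difference with a Miettinen-Nurminen 95% score interval.
- Name one test in advance: the score test that matches this interval, so that test and interval agree. Leaving score or Fisher open would not settle the analysis, since they give 0.041 and 0.117 for 0 vs 4. The Miettinen-Nurminen form multiplies the score statistic by 89/90 here, so its error cannot exceed that of the score test in the table.
- If adjustment for route is wanted, use Firth-penalised logistic regression.

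The cost is one paragraph of analysis text, with no new data and no more patients. The small loss is that the rarest items will have no ordinary route-adjusted odds ratio. The plan names JMP 12 for all analyses; the sponsor should check that it offers these methods, or name a second package.
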